Study Endpoint	The primary outcome variable will be the OAB-q symptoms severity subscale score (urinary symptom questionnaire) as a marker of efficacy. The secondary outcome variables will include UTI rate, PVR, urinary retention, inter-injection interval, catheter use within 3 months, PGI-I, and VAS pain score.		
Statistical Methods	The target sample size was determined by using the typical standard deviation of the OAB-q score (20 points per literature review) and the known minimally important clinical difference of 10 points of the OAB-q severity subscale, our primary outcome. Using this data, we calculated the sample size of N=102 maximum total (expect to enroll ~40 at KP, ~60 at UCI, ~20 at PSJH), 51 subjects in each arm for a 80% power with 5% significance level. With an estimated 15% lost to follow up rate, we calculated need to enroll 116 subjects.		

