# 3 STUDY DESIGN

We plan for a prospective, single-blinded, non-inferiority randomized controlled trial. We will evaluate the efficacy, safety, and tolerability of one intradetrusor Botox® injection (study) versus ten injections (control/standard of care). The patient will be blinded. There will be 1:1 randomization. The physician doing the procedure will not be blinded.

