# 3.1 Treatment Arms

There will be two arms for this trial: study arm (one injection) and control arm (10 injections). Across all sites we will plan to enroll 116 maximum participants with anticipated enrollment at Kaiser Permanente being approximately 40 participants.

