# 12 STATISTICAL CONSIDERATIONS

# 12.1 Study Hypothesis

We hypothesize that one intradetrusor Botox® injection site has similar efficacy to ten injections sites based on OAB-Q symptoms severity score change from pre-procedure to 3-week post-procedure with a minimal clinical important difference of 10.

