### 12.2 Sample Size Considerations

The target sample size was determined by using the typical standard deviation of the OAB-q symptom severity score (20 points per literature review) and the known minimally important clinical difference of 10 points of the OAB-q severity subscale, our primary outcome. Using this data, we calculated the sample size of N=102 maximum total (expect to enroll ~40 at KP, ~60 at UCI, ~20 PSJH), 51 subjects in each arm for an 80% power with 5% significance level. Based on review of prior clinical data at UCI and KP, we expect to complete enrollment within 1 – 1.5 years. With an estimated 15% lost to follow up rate, we calculated need to enroll 116 subjects.

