### 12.3 Final Analysis Plan

We will describe the study population, including patient age, race/ethnicity, baseline severity scores (OAB-Q), BMI, medical history (prior surgery, menopausal status, prior Botox, etc.), overall, by arm, and stratified by study site (KPSC, UCI, PSJH). We will summarize continuous measures using means and standard deviations and categorical measures using percentages. We will compare study arms using the t-test or Fisher's exact test, as appropriate.

We will examine the outcome measures (OAB-Q and any secondary measures) to determine whether they are approximately normally distributed. If not, we will apply a

transformation prior to analysis to make the analytic variable approximately normal. If no transformation successfully achieves approximate normality, we will apply non-parametric tests for analysis, including Wilcoxon's rank-sum test instead of the t-test and quantile regression instead of linear regression.

We will analyze the main study outcome (OAB-Q score) initially using a t-test to compare the two study arms, overall and stratified by study site. We will further analyze the outcome using generalized estimating equations to account for correlation within study sites. These models will adjust for any potential differences in age, race/ethnicity, baseline severity scores, or any other baseline measures, and will account for any potential differences between study sites.

Secondary outcomes will be analyzed in the same manner as the primary outcome.

Primary analyses will be performed using intention-to-treat to determine study arm. If multiple individuals are not treated according to the randomization plan, we will perform a sensitivity analysis using as-treated, per-protocol study arms.

For any individuals who are lost to follow-up, we will first compare those individuals who are lost to those who complete follow-up in terms of demographics, baseline characteristics and any outcome assessments prior to the time that they are lost to follow-up. For primary analysis of OAB-Q scores, we will analyze complete data including only those who have completed the follow-up questionnaires within the prescribed timeframes. If more than 10% are lost to follow-up, we will additionally perform multiple imputation in an attempt to capture data of those lost to follow-up.

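### The enrolment figure of 116 does not follow from 102 evaluable and 15% loss (120 is needed), and the one-sided 5% criterion behind 51 per arm is not written down

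*Combined protocol and SAP*

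**What the plan says.** Section 3 declares the design: "We plan for a prospective, single-blinded, non-inferiority randomized controlled trial". Section 12.2 takes an SD of 20 points and a minimally important difference of 10 points on the OAB-q symptom severity subscale, and arrives at "51 subjects in each arm for an 80% power with 5% significance level". It then inflates for attrition: "With an estimated 15% lost to follow up rate, we calculated need to enroll 116 subjects".

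Three totals are in circulation:

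- The Protocol Summary has "we calculated the sample size of N=102 maximum total", and section 12.2 repeats that label.
- Section 3.1 has "Across all sites we will plan to enroll 116 maximum participants".
- The approximate site targets, given in the summary and in section 12.2, are 40, 60 and 20.

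On the criterion, section 12.1 hypothesises similar efficacy on the change from pre-procedure to 3 weeks, "with a minimal clinical important difference of 10". Section 12.3 analyses the main outcome "initially using a t-test to compare the two study arms", followed by adjusted generalized estimating equation models. For missing data the primary rule is that "we will analyze complete data including only those who have completed the follow-up questionnaires within the prescribed timeframes". Multiple imputation is added only if loss exceeds 10%.

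**The concern.** There are two separate gaps in the sample size reasoning.

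First, the inflation from 102 to 116 does not match the stated 15% loss. Because the primary analysis uses completers only, the shortfall falls directly on the analysed number. The text also calls both 102 and 116 a maximum, while the site targets add to a third figure.

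Second, a 5% significance level without a side does not define a non-inferiority test. The 10 points is described as a clinically important difference and never as the non-inferiority margin. A t-test comparing arms, as named in section 12.3, tests for a difference from zero; failing to find one does not establish non-inferiority. The analyst has no written confidence level, limit or margin to apply, so the choice between a 90% and a 95% interval could be made after the data are seen. The stated 80% power belongs to only one of those choices.

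**Working it through.** **Inputs.** SD 20, difference 10, power 80%, significance level 5%, 51 per arm, loss 15%, enrolment 116 (all section 12.2); cap of 116 (section 3.1); 1:1 allocation and non-inferiority design (section 3); complete-case primary analysis (section 12.3). Assumptions of this check: the SD of 20 applies to the variable analysed, the true difference is 0, and the 10 points serves as the margin.

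**Step 1: reproduce 51 per arm.** By normal approximation, n per arm = 2 × (z for alpha + z for power)² × SD² / margin².

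- One-sided 5%: 2 × (1.645 + 0.842)² × 400/100 = 49.5, so 50.
- One-sided 2.5%: 2 × (1.960 + 0.842)² × 400/100 = 62.8, so 63.

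With the noncentral t distribution, the smallest n per arm reaching 80% is 51 at one-sided 5% (50 gives 79.9%, 51 gives 80.6%) and 64 at one-sided 2.5%. The plan's 51 is therefore the exact t-test answer for one-sided 5%.

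**Step 2: enrolment.**

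- Needed: 102 / (1 − 0.15) = 120.0, or 60 per arm.
- Delivered by 116: 116 × 0.85 = 98.6, about 49 per arm.
- Loss that 116 can absorb while leaving 102: 1 − 102/116 = 12.1%.
- Multiplying instead of dividing, a common slip, gives 102 × 1.15 = 117.3, which is near 116 but not equal to it.
- Site targets: 40 + 60 + 20 = 120.

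**Step 3: power (noncentral t, same assumptions).**

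| Evaluable per arm | One-sided 5% (90% CI) | One-sided 2.5% (95% CI) |
|---|---|---|
| 51 / 51 | 80.6% | 70.6% |
| 50 / 49 | 79.5% | 69.2% |
| 49 / 49 | 79.2% | 68.8% |

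The inflation slip costs about 1 point, whichever column applies. Moving from the first column to the second costs about 10 points.

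**Step 4: what the unstated side does to the conclusion.** At 51 per arm the standard error is 20 × √(2/51) = 3.96.

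- 90% CI half-width: 1.660 × 3.96 = 6.58. The largest observed disadvantage that passes is 10 − 6.58 = 3.42 points.
- 95% CI half-width: 1.984 × 3.96 = 7.86. The largest that passes is 10 − 7.86 = 2.14 points.

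Any observed disadvantage between those two values, roughly 2.2 to 3.4 points, is declared non-inferior under one rule and not under the other.

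**Step 5: chance of reaching 102 completers.** With independent 15% loss, the binomial probability of at least 102 completers is 23% from 116 enrolled and 56% from 120. This only illustrates the gap. The plan sets no such requirement, and power changes smoothly around 102.

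**The case against.** The strongest reply is that the enrolment error is nearly immaterial. Power under the sizing criterion falls less than one point below the 80% target. The 15% is only an estimate and is not tied to a time point; since the primary comparison is at 3 weeks and follow-up runs to 3 months, loss at 3 weeks could be lower. The site targets are approximate, so their adding to 120 does not strictly contradict a cap of 116, and the order of reasoning in section 12.2 makes clear that 102 comes first and is then inflated. All of this is fair on size. It does not make 116 the result of 102 and 15%.

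On the criterion, one can argue that a one-sided 5% test against 10 points can be recovered from the plan, because 51 reproduces exactly and the design is declared non-inferiority. That is true, and the sizing itself is not wrong. But a criterion recovered by back-calculation is not a pre-specified decision rule, and section 12.3, which governs the analysis, contains none.

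The power figures also depend on the SD. At 51 per arm and one-sided 2.5%, power would be 82% with an SD of 17.3 and 62% with an SD of 22. The plan analyses a change and later adjusts for baseline, so the effective SD could differ from 20. This caveat stands and should accompany the figures.

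Finally, going to 120 raises a cap stated in a protocol that goes to the IRB, so it is more than a wording change. That stands too, and it is why keeping 116 with restated figures is offered below.

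**Conclusion.** Both parts hold. The stated enrolment is 4 short of what the plan's own inputs require (116 against 120), leaving about 98 or 99 evaluable rather than 102. Taken alone this is a small slip worth about 1 point of power.

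The more consequential gap is that the 80% power depends on a one-sided 5% test against a 10-point margin, and the plan states neither the side nor the margin. Under a two-sided 95% interval the same trial has about 69% to 71% power.

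The enrolment arithmetic needs no assumption beyond the plan's own 102 and 15%. The power figures assume SD 20 for the analysed variable and no true difference between arms. Nothing here says that one-sided 5% is the wrong choice, only that it has to be written down. This should be fixed before analysis.

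**What to change.** **Enrolment (section 12.2, section 3.1, Protocol Summary).** Label 102 as the number evaluable and remove the word maximum from it. Then do one of the following:

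- Replace 116 by 120. This equals the sum of the site targets, but it raises the cap in section 3.1 and so needs a protocol amendment.
- Keep 116 and say what it delivers: about 98 evaluable and 79% power at 15% loss, or 102 evaluable if loss is no more than 12%. This is text only.

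**Criterion (sections 12.2 and 12.3).** Name 10 points as the non-inferiority margin, state the assumed true difference of 0, and give one decision rule used for both sizing and analysis. There are two consistent choices:

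- One-sided 5%, equivalently a two-sided 90% confidence interval compared with the margin. This matches the existing 51 per arm and changes no number.
- A two-sided 95% interval. Either restate power as about 71% with 102 evaluable or 69% with 98, or resize to 64 per arm, which is 128 evaluable and 128/0.85 = 150.6, so 151 enrolled.

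Apart from that last option and any rise in the cap, the cost is a few sentences.

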### 12.3 Final Analysis Plan

We will describe the study population, including patient age, race/ethnicity, baseline severity scores (OAB-Q), BMI, medical history (prior surgery, menopausal status, prior Botox, etc.), overall, by arm, and stratified by study site (KPSC, UCI, PSJH). We will summarize continuous measures using means and standard deviations and categorical measures using percentages. We will compare study arms using the t-test or Fisher's exact test, as appropriate.

We will examine the outcome measures (OAB-Q and any secondary measures) to determine whether they are approximately normally distributed. If not, we will apply a

transformation prior to analysis to make the analytic variable approximately normal. If no transformation successfully achieves approximate normality, we will apply non-parametric tests for analysis, including Wilcoxon's rank-sum test instead of the t-test and quantile regression instead of linear regression.

We will analyze the main study outcome (OAB-Q score) initially using a t-test to compare the two study arms, overall and stratified by study site. We will further analyze the outcome using generalized estimating equations to account for correlation within study sites. These models will adjust for any potential differences in age, race/ethnicity, baseline severity scores, or any other baseline measures, and will account for any potential differences between study sites.

Secondary outcomes will be analyzed in the same manner as the primary outcome.

Primary analyses will be performed using intention-to-treat to determine study arm. If multiple individuals are not treated according to the randomization plan, we will perform a sensitivity analysis using as-treated, per-protocol study arms.

For any individuals who are lost to follow-up, we will first compare those individuals who are lost to those who complete follow-up in terms of demographics, baseline characteristics and any outcome assessments prior to the time that they are lost to follow-up. For primary analysis of OAB-Q scores, we will analyze complete data including only those who have completed the follow-up questionnaires within the prescribed timeframes. If more than 10% are lost to follow-up, we will additionally perform multiple imputation in an attempt to capture data of those lost to follow-up.

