# PROTOCOL SUMMARY

Title	Intradetrustor Botulinum Toxin A: Are less injections better?			
Short Title	Bladder Botox			
Protocol Number	KPSC-US-01			
Study Phase	N/A			
Study Site(s)	Kaiser Permanente – Sand Canyon, Kaiser Permanente -Anaheim, UCI			
Number of Subjects	Approx 40 at KPSC, 60 at UCI, 20 at PSJH			
Study Arms	2 arms: One Botox® injection site (study) or 10 Botox® injection sites (control/standard of carl)			
Indication	Overactive Bladder (Urinary urgency and frequency) and urinary urgency incontinence			
Primary Purpose	Our primary objective is to evaluate the efficacy of intradetrusor Botox® for treatment of OAB or UUI based on patient questionnaire scores (OAB-q) in one versus ten Botox® injection [s].			
Overview of Study Design	We plan for a prospective, single-blinded, non-inferiority analyzed, randomized controlled trial. We will evaluate the efficacy, safety, and tolerability of one intradetrusor Botox® injection (study) versus ten injections (control/standard of care). The patient will be blinded . There will be 1:1 randomization.			
Investigational Product Administration	Not applicable, no investigational product.			
Eligibility Criteria	Inclusion criteria: Female, at least 18 years old with diagnosis of overactive bladder (urinary urgency or frequency, OAB) or urinary urgency incontinence (UUI) Exclusion criteria:			
	
 
Have a diagnosis of neurogenic bladder
 
Received intravesical botox injections within prior 6 months
 
Current treatment with either: SNM, PTNS, or OAB medications – need wash out as below
 
SNM – turn device off for at least 2 weeks prior to procedure, off during 3-month follow up window
 
PTNS – no treatments within 2 weeks of start, none during 3-month post-procedure follow up window
 
OAB meds – 2 week wash out period prior to injection, none during 3-month post-procedure follow up window
 
			

	
 
Currently pregnant or trying to get pregnant
 
Contraindications to Botox® - hypersensitivity to Botox®, inability to self-catheterize/refusal to have indwelling catheter
 
Have a UTI (can enroll after treatment)
 
Have urinary retention (PVR>150cc on two occasions)
 
Do not speak English or Spanish
 
		

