# 1.2 Hypothesis

We hypothesize that one injection of intradetrusor Botox® will have similar efficacy to ten injections, better tolerability, due to decreased procedure time and less pain, along with potential for lower adverse event rates, specifically urinary retention and urinary tract infections.

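### The trial is described as non-inferiority, but section 12.3 gives no margin, direction, sidedness or confidence-limit rule, names no decisive analysis, and allows a transformation that would leave the 10-point scale

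*Combined protocol and SAP*

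**What the plan says.** The Protocol Summary states "We plan for a prospective, single-blinded, non-inferiority analyzed, randomized controlled trial", and section 3 repeats the design: "We plan for a prospective, single-blinded, non-inferiority randomized controlled trial". Section 1.2 hypothesises that one injection "will have similar efficacy to ten injections, better tolerability". Section 12.1 ties the efficacy hypothesis to the change in symptom severity from "pre-procedure to 3-week post-procedure with a minimal clinical important difference of 10". Section 12.2 uses the same 10 points and an SD of 20 to reach "51 subjects in each arm for an 80% power with 5% significance level". Both sections call the 10 points a minimal important difference. Neither calls it a margin, and section 12.2 does not say whether the 5% is one-sided or two-sided.

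Section 12.3 is the only analysis plan. It says "We will analyze the main study outcome (OAB-Q score) initially using a t-test to compare the two study arms", and then "We will further analyze the outcome using generalized estimating equations to account for correlation within study sites", with adjustment for baseline measures and site. If the outcome is not approximately normal, the first step is a "transformation prior to analysis to make the analytic variable approximately normal". If that does not work, the rank-sum test replaces the t-test and quantile regression replaces linear regression. Section 12.3 speaks of primary analyses only when it sets the intention-to-treat arm and the complete-case data set, not when it chooses the test.

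**The concern.** A non-inferiority conclusion needs a margin, a direction, an error level and a rule linking a confidence limit or a shifted test to that margin. Section 12.3 has none of these. It lists two analyses of the same outcome and gives their order, but does not say which one decides. Someone following it to the letter would obtain a comparison of the arms but no basis for declaring similar efficacy.

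The fallbacks add to the problem. The type of transformation is left open, with no back-transformation and no restated margin. The rank-sum test gives no difference in points. Quantile regression stays in points but has no margin attached.

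At stake is the trial's main conclusion, which could turn on the model, scale or confidence level chosen after the data are seen.

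**Working it through.** **Inputs.** Difference 10 points (sections 12.1, 12.2). SD 20 (section 12.2; given for the score, taken here for the 3-week change). Power 80%, level 5%, sidedness not stated, 51 per arm, 116 to enrol, 15% loss (section 12.2). Allocation 1:1 (section 6). A deficit means that one injection does worse than ten by that many points.

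**1. Reproduce the sample size.** With a true difference of 0, n per arm = 2 × (20/10)² × (z₁₋α + z₀.₈₀)².
- One-sided 5%: 8 × (1.645 + 0.842)² = 49.5, so 50. The noncentral t gives 51, with 80.6% power.
- One-sided 2.5% or two-sided 5%: 8 × (1.960 + 0.842)² = 62.8, so 63. The noncentral t gives 64.

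The plan's 51 therefore fits a one-sided 5% test against 10 points. This is an inference, because a one-sided superiority test for 10 points gives the same number.

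**2. Power if 10 points is the margin** (116 × 0.85 = 98.6, about 49 per arm).

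| Per arm | One-sided 5% | One-sided 2.5% |
|---|---|---|
| 51 | 80.6% | 70.6% |
| 49 | 79.2% | 68.8% |

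**3. Where the two readings of the t-test part.** At 51 per arm, SE = 20 × √(2/51) = 3.96.
- 90% CI half-width: 1.660 × 3.96 = 6.58. Non-inferiority needs an observed deficit below 10 − 6.58 = 3.42.
- 95% CI half-width: 1.984 × 3.96 = 7.86. A two-sided t-test is non-significant below 7.86.

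Observed deficits from about 3.4 to 7.9 points are thus non-significant but fail non-inferiority.

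**4. Chance of passing under each reading** (51 per arm, SD 20).

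| True deficit | p > 0.05, two-sided | Non-inferiority, one-sided 5% |
|---|---|---|
| 5 | 76.0% | 34.8% |
| 7.5 | 53.4% | 15.4% |
| 10 | 29.4% | 5.0% |

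With an assumed SD of 15 or 25, the 29.4% becomes 8.5% or 48.4%.

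**5. Transformation.** On a log scale, 10 points above illustrative control scores of 20, 40 and 60 is ln(30/20) = 0.41, ln(50/40) = 0.22 and ln(70/60) = 0.15. After a nonlinear transformation 10 points has no single equivalent.

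**6. Which analysis decides.** Simulation with 12,000 trials per setting. Assumed: 34/50/18 evaluable by site, following the 40:60:20 enrolment split; arms balanced within site; normal outcome; no site effect; baseline correlation with outcome 0, 0.3 or 0.5; GEE adjusted for baseline. Each analysis is compared with 10 points by a 90% CI. Chance of passing at a true 10-point deficit:
- t-test: 4.9% to 5.1%.
- Linear model with baseline, site as a fixed effect and model-based standard errors: 5.0% to 5.4%.
- GEE with model-based standard errors: 5.2% to 5.5%.
- GEE with an uncorrected sandwich variance on three sites: 16.4% to 17.4%.

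At that deficit the t-test and the sandwich GEE disagree in 12% to 14% of trials. In a separate run of 8,000 trials per setting, the t-test and the model-based GEE disagreed in 0.7%, 2.3% and 4.4% for the three correlations. With no true difference, they disagreed in 1.7%, 6.3% and 11.9%.

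**The case against.** The best defence is that the intent can be recovered. The Protocol Summary says the trial will be analysed for non-inferiority, section 12.1 attaches 10 points to the hypothesis, the sample size fits a one-sided 5% test, and a t-test can be run against a shifted null. Non-inferiority of the study arm to the control is also directional in itself. This stands as a reading of intent, and it makes the repair easy. It does not supply the rule: no section calls 10 points a margin or gives the sidedness, and a decision rule deduced from a sample size has not been prespecified.

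Three stronger inferences are tempting, and the documents do not support them.
- A reader might infer that the trial will treat p > 0.05 as similarity and so carry a 29% error. The plan neither says nor excludes this, and the non-inferiority label points the other way. The figure is conditional.
- A reader might infer that the planned GEE inflates the error to 16% to 17%. That needs an uncorrected sandwich variance, and section 12.3 names no variance. With model-based errors the GEE holds about 5%.
- A reader might infer that the transformation always defeats the 10-point comparison. It applies only if normality fails, and a linear rescaling would do no harm. The problem is an unspecified nonlinear transformation without a restated margin.

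It is also fair to say that the t-test alone, compared with the margin, would be a valid decisive analysis. Preferring the adjusted model is a matter of efficiency, not validity.

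**Conclusion.** The point holds and should be settled before outcomes are compared by arm. As written, section 12.3 does not carry out the non-inferiority comparison that the design sections announce, and it does not say which of its analyses decides. This is more than missing detail, because following the plan would not answer the trial's question.

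The firm measure of its size is the band of observed deficits, about 3.4 to 7.9 points, in which a non-significant two-sided t-test and a failed non-inferiority test occur together. It rests on SD 20 for the 3-week change, 51 per arm, one-sided 5% and 10 points as the margin. The last two are inferred from the documents, not stated there. The sample size itself is not shown to be wrong by this point: it agrees with a one-sided 5% rule that the plan never writes down.

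**What to change.** Amend section 12.3 as follows.
1. State 10 points on the OAB-q symptom severity subscale as the non-inferiority margin for the 3-week change, if that is what is intended. Give its direction and a short justification, since it equals the whole minimal important difference.
2. Name one decisive analysis on the original scale. A linear model adjusted for baseline severity, with site as a fixed effect and model-based standard errors, is preferable; the t-test is also valid but gains nothing from baseline. Make the other analyses supportive, and do not let a GEE with an uncorrected sandwich variance on three sites decide.
3. Conclude non-inferiority only if the limit of the two-sided 90% CI unfavourable to one injection is inside 10 points.
4. Drop the transformation and rank-sum steps from the decisive analysis. Keep any bootstrap or non-parametric result as a sensitivity analysis only, so that there is a single decisive interval.
5. State the one-sided 5% level and its unadjusted power: 80.6% at 51 per arm, and 79.2% at the 49 per arm left after 15% loss from 116.

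The cost is wording only, with no added patients at one-sided 5%. Simulated power of the fixed-site model is 80.1%, 83.4% or 89.1% at 102 evaluable for baseline correlations of 0, 0.3 or 0.5 (assumed), and 78.2%, 82.3% or 87.8% at 98 evaluable.

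The downside is that one-sided 5% is lenient. If one-sided 2.5% is preferred, restate the power as about 71% at 51 per arm (69% at 49). Restoring 80% would take 64 per arm: 128 evaluable, or 128/0.85 = 150.6, about 151 enrolled.

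### The follow-up GEE on the main outcome clusters on only three sites with no SE method given; with an uncorrected sandwich SE its false non-inferiority rate would be about 17-18%, not 5%

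*Combined protocol and SAP*

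**What the plan says.** Section 12.3 (Final Analysis Plan) sets out two analyses of the main outcome. The first is unadjusted: "We will analyze the main study outcome (OAB-Q score) initially using a t-test to compare the two study arms, overall and stratified by study site". The second follows it: "We will further analyze the outcome using generalized estimating equations to account for correlation within study sites". On covariates the plan says "These models will adjust for any potential differences in age, race/ethnicity, baseline severity scores, or any other baseline measures", and adds that the models "will account for any potential differences between study sites". The sites are listed earlier in the same section, where the population is to be described "overall, by arm, and stratified by study site (KPSC, UCI, PSJH").

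The section does not give the working correlation, the variance estimator, any small-sample correction or the reference distribution for the GEE. It does not say whether the t-test or the GEE decides non-inferiority. It speaks of primary analyses only when fixing intention-to-treat assignment and complete-case data. It then extends the approach: "Secondary outcomes will be analyzed in the same manner as the primary outcome".

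Section 12.2 gives "51 subjects in each arm for an 80% power with 5% significance level", with SD 20 and a difference of 10, and site sizes "expect to enroll ~40 at KP, ~60 at UCI, ~20 PSJH". Section 6 describes individual 1:1 randomisation in permuted blocks.

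**The concern.** GEE is usually reported with the robust (sandwich) SE, which estimates variance from the spread of cluster-level contributions and is valid when there are many clusters. Here the cluster is the study site, and there are three. The estimate then rests on about two independent pieces of information and is biased downward. Normal critical values ignore both problems. This happens even when sites do not differ at all, and adding site terms to the model does not cure it.

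In a non-inferiority trial, an SE that is too small makes it easier to accept a treatment that is worse by the whole margin. The adjusted result could be favourable where the t-test is not, and no rule covers that conflict.

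Clustering on site is also not needed for the arm comparison. Patients are randomised individually, both arms are expected at every site, and the plan itself compares arms within site. Site differences can be handled by a fixed effect.

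**Working it through.** **1. The plan's own figure.** Inputs from section 12.2: SD 20, difference 10, power 80%, level 5% (sidedness not stated).

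- One-sided 5%: n = 2(1.645 + 0.842)² × 20²/10² = 8 × 6.18 = 49.5, so 50 per arm. The exact noncentral t gives 79.9% power at 50 and 80.6% at 51. The stated 51 is therefore a two-sample t-test at one-sided 5%.
- One-sided 2.5%: 8 × (1.960 + 0.842)² = 62.8, so 63 by this formula (64 by the exact t). With 51 per arm the power is about 71%.

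**2. Hand check with three equal, balanced sites and no covariates.** Let d₁, d₂, d₃ be the arm differences within each site.

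- The arm effect is their mean. The uncorrected sandwich variance is Σ(dₖ − d̄)²/3². The unbiased version is Σ(dₖ − d̄)²/(3 × 2). The ratio is 2/3.
- The correctly scaled statistic follows t on 2 df. Using 1.645 with the uncorrected SE amounts to comparing t₂ with 1.645 × √(2/3) = 1.343.
- P(t₂ > c) = ½[1 − c/√(2 + c²)] = ½[1 − 1.343/1.950] = 15.6%. For one-sided 2.5%, c = 1.960 × √(2/3) = 1.600 and the result is 12.5%.
- The median of χ²₂/2 is 0.693, so the median SE is √(0.667 × 0.693) = 0.68 of the true value.

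Simulation with three sites of 34 gave 15.0-16.2% and 12.2-13.0%, with median ratios of 0.67-0.69, in agreement. Unequal sites make it somewhat worse.

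**3. Simulation at the planned site sizes.** The 40/60/20 in section 12.2 sums to 120. Scaled to 102 it gives 40 × 102/120 = 34, 60 × 102/120 = 51 and 20 × 102/120 = 17. Assumptions: true deficit 10 = margin, SD 20, baseline correlation 0.5, site SD 0 or 5, age and a four-level race/ethnicity covariate, blocks of 4 within or across sites, N of 102 or 116. There were 10,000 trials per scenario over seven three-site scenarios, with and without site terms. Nominal level: one-sided 5%.

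| Method | False non-inferiority |
|---|---|
| Sandwich SE, normal reference | 17.2-17.6% |
| Model-based SE, t reference | 4.7-5.6% |
| Individual-level HC3 SE, t reference | 4.2-4.9% |
| t-test on change | 4.7-5.3% |
| Sandwich claims non-inferiority, t-test does not | 13.4-13.8% |

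- The median sandwich SE was 0.61-0.63 of the true value. Simpler models gave about 0.64 of the model-based SE.
- Other runs gave 16-18% for the sandwich. With baseline and site only, the rate was 16.7%. A packaged GEE routine gave 17.2-17.5% robust and 5.4-5.9% model-based with the planned covariates, and 16-17% robust with simpler models.
- At one-sided 2.5%, the sandwich gave about 14% and the model-based SE about 2.5%.
- If the two Kaiser locations in the Protocol Summary were separate clusters (assumed 17/17/51/17), the rates at one-sided 5% were about 14% and 5%.

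**4. Repairs to the sandwich.** One correction alone is not reliably enough: t on 2 df gave 8.0-8.6%, and K/(K−1) scaling with a normal reference gave 13.4-14.0%. The two together gave 5.7-6.2%.

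**5. Power at no true difference, one-sided 5%.** This depends on the baseline correlation, which the documents do not give. With SD 20 taken as the SD of the score and the correlation varied from 0.2 to 0.8:

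| Method | Power |
|---|---|
| Linear model with site and baseline | about 81-99% |
| t-test on change | about 64-99% |
| K/(K−1) sandwich with t on 2 df | about 55-84% |

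**6. Continuous secondary outcomes.** A two-sided 5% test rejected a true null in 27.6-28.6% of trials with the uncorrected sandwich and 4.5-5.2% with the model-based SE.

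**The case against.** The strongest reply is that the plan never commits to the sandwich SE. Model-based SEs fit the text equally well and hold the error rate. The GEE is introduced as a further analysis after the t-test, and the sample size is the t-test's. On that reading the GEE is supportive and the trial's main conclusion carries no inflation. This stands. A reader might infer that the primary analysis has a 17% error rate; the documents do not support that.

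It is also fair that no confidence-limit rule or sidedness is stated, and that the 10 points are never called a margin. The percentages are conditional on those readings. The direction is not: at either level the sandwich rate is more than three times the nominal one.

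Two further inferences fail. One is that a corrected sandwich must take power below the planned 80%. It may or may not, depending on the baseline correlation. The other is that the same inflation applies to every secondary outcome. UTI rate, retention and catheter use are not plainly continuous, and nothing was computed for them.

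What remains is that one sentence of the plan admits error rates of about 5% and about 17%, the higher from the usual GEE default, and nothing says which analysis prevails if the two disagree.

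**Conclusion.** The point holds as a should-fix weakness in the adjusted analysis, not as a flaw in the t-test. Three sites are too few for an uncorrected sandwich SE. If that SE is used with normal critical values, false non-inferiority is about 17-18% at one-sided 5%, or about 14% at one-sided 2.5%, instead of about 5% or 2.5%. At one-sided 5%, about 13-14% of trials with a true 10-point deficit would show non-inferiority by the GEE and not by the t-test.

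This rests on the 10-point difference serving as the margin, SD 20, site sizes near the expected ones, and an SE choice that the plan leaves open. It does not rest on any correlation within sites, since the inflation is there with none. Confidence in the size of the effect, given that choice, is high. Whether the sponsor would make that choice cannot be known from the documents.

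**What to change.** In section 12.3, replace the site-clustered GEE with a linear model for the 3-week OAB-q symptom severity score. Include arm, site as a three-level fixed effect, baseline score, and the covariates already planned (age, race/ethnicity). Use model-based or individual-level heteroscedasticity-consistent SEs with a t reference. With baseline in the model, the arm effect is the same whether score or change is the outcome. The section already mentions linear regression when it gives its non-parametric fallback, so this is close to the existing text.

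State whether this model or the t-test decides non-inferiority.

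If GEE is kept, put site in the mean model and specify model-based SEs, not an uncorrected sandwich over three clusters. For secondary outcomes, use site as a fixed effect or stratification factor.

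The cost is SAP wording and 2 of about 100 degrees of freedom, with no extra patients or data.
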